#### 2.4.2 Secondary Endpoints

All secondary endpoint analyses will be performed on the FAS.

##### 2.4.2.1 Pulmonary Function Tests

###### 2.4.2.1.1 Derivation of Pulmonary Function Tests

Pulmonary function test results will be recorded in the data at baseline and at the end of each month of therapy during the active treatment period. During these visits, the following procedures and assessments will be conducted:

- Slow Vital Capacity (SVC)
- Peak Cough Flow (PCF)

- Resting Oxygen Saturation (SPO2)
- Maximal Inspiratory Pressure (MIP)

#### **2.4.2.1.2 Analysis of Pulmonary Function Tests**

Pulmonary function tests (SVC, PCF, SPO2, MIP) that were acceptable by ATS Standards, deemed the 'Best Measurements' for the series based on ATS acceptability, and completed in accordance with the study protocol will be analyzed descriptively at each time-point (Baseline, 1-month, 2-month, 3-month, 4-month, 5-month, 6-month), using n, mean, standard deviation, minimum, median, and maximum. Change from baseline values will also be presented in a similar manner. Subjects with SPO2 measures collected in the same setting across all study visits will be tabulated. SPO2 measures across all settings will be listed.

#### **2.4.2.2 Number of Hospital Admissions**

##### **2.4.2.2.1 Derivation of Number of Hospital Admissions**

The number of hospital admissions that occurred during the pre-treatment period and active treatment period will be recorded in the data.

##### **2.4.2.2.2 Analysis of Number of Hospital Admissions**

The number of hospital admissions will be analyzed descriptively by study period (active treatment and 6-month pre-treatment) using n, mean, standard deviation, minimum, median, and maximum. All hospital admissions that occurred in the 12-month pre-treatment period and the active treatment period will be listed.

#### **2.4.2.3 Hospital Length of Stay**

##### **2.4.2.3.1 Derivation of Hospital Length of Stay**

Total hospital length of stay will be determined for each study subject by calculating the number of days spent in the hospital for each admission, from time of admission to time of discharge. Date of admission and date of discharge will be recorded in the data for each study period. The sum of all hospital days for each subject will be calculated for the 6-month pre-treatment and active treatment periods. The number of days spent in the hospital for each admission will be calculated as follows (standardized to the number of days):

*Date of Discharge – Date of Admission + 1*

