| | | |
|---------------|-------------------------|-------|
| Printed Name: | Investigator Signature: | Date: |
|---------------|-------------------------|-------|

PROTOCOL TITLE

Evaluation of Oscillation and Lung Expansion (OLE) using The Volara® System for treatment of respiratory complications in patients with neuromuscular disease in the home setting

Final Protocol

Protocol Number: CR-RR-2020-005

Date: 11May2022

Protocol Synopsis

| | |
|-------------------------|---|
| Protocol Title: | Evaluation of Oscillation and Lung Expansion (OLE) using The Volara® System for treatment of respiratory complications in patients with neuromuscular disease in the home setting |
| Protocol Number: | CR-RR-2020-005 |

PROTOCOL TITLE

Evaluation of Oscillation and Lung Expansion (OLE) using The Volara® System for treatment of respiratory complications in patients with neuromuscular disease in the home setting

Final Protocol

Protocol Number: CR-RR-2020-005

Date: 11May2022

| | |
|----------------------|--|
| Device Name(s): | The Volara® System |
| Sponsor: | Hill-Rom Company, Inc. [name] |
| Objective(s): | Evaluation of the impact of Oscillation and Lung Expansion (OLE) therapy to treat respiratory complications of neuromuscular disease patients |
| Endpoints: | Primary Endpoint: 
● Frequency of exacerbations of pulmonary disease requiring medical intervention (e. g. one or more of the following):¹
○ Hospitalization○ ED Visit○ Unscheduled Antibiotics for Respiratory Infection○ Unscheduled outpatient visit Secondary Endpoints: 
● Pulmonary function tests
○ Slow Vital Capacity (SVC)○ Peak Cough Flow (PCF)○ Resting Oxygen Saturation (SPO2)○ Maximal Inspiratory Pressure (MIP)● Number of individual hospitalizations● Number of inpatient hospital days● Number of ICU admissions● Number of ICU days● Number of outpatient visits for pulmonary complication (Unscheduled Physician's office, Urgent Care Visits, ED visits)● Number of antibiotic use days during episodes of pneumonia
○ IV antibiotic days○ Oral antibiotic days |

PROTOCOL TITLE

Evaluation of Oscillation and Lung Expansion (OLE) using The Volara® System for treatment of respiratory complications in patients with neuromuscular disease in the home setting

Final Protocol

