3.3.4.2 Secondary Endpoint(s):**• Hospital Admissions**

Total number of Hospital Admissions will be determined for each study subject by review of the medical record for pre-treatment period and for the active treatment period. Total Hospital Admissions will be determined for each subject and for the study group (Mean \pm SD) for each study period.

• Hospital Length of Stay

Total Hospital Length of Stay will be determined for each study subject by calculating the number of days spent in the hospital for each admission, from time of admission to time of discharge. The sum of all hospital days for each subject will be calculated for the pre-treatment period and for the active treatment period. Total Hospital Days will be determined for each subject and for the study group (Mean \pm SD) for each study period.

• ICU Admissions

Total number of ICU Admissions will be determined for each study subject by review of the medical record during the pre-treatment period and for the active treatment period. Total ICU Admissions will be determined for each subject and for the study group (Mean \pm SD) for each study period.

• ICU Length of Stay

Total ICU Length of Stay will be determined for each study subject by calculating the number of days spent in the ICU for each admission, from time of admission to time of discharge. The sum of all ICU days for each subject will be calculated for the pre-treatment period and for the active treatment period. Total ICU Days will be determined for each subject and for the study group (Mean \pm SD) for each study period.

• Number of Outpatient Visits

PROTOCOL TITLE

Evaluation of Oscillation and Lung Expansion (OLE) using The Volara® System for treatment of respiratory complications in patients with neuromuscular disease in the home setting

Final Protocol

Protocol Number: CR-RR-2020-005

Date: 11May2022

Total number of Outpatient Visits will be determined for each study subject by review of the medical record and identifying all visits defined as 1) physician office visits, 2) urgent care visits or 3) emergency department (ED) visits for pulmonary complications that occur during the pre-treatment period and during the active treatment period. Total Outpatient Visits will be determined for each subject and for the study group (Mean \pm SD) for each study period.

● Number of Antibiotic Use Days

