#### **2.4.2.5 ICU Length of Stay**

##### **2.4.2.5.1 Derivation of ICU Length of Stay**

Total ICU length of stay will be determined for each study subject by summing the calculated number of days spent in the ICU for each admission, from time of admission to time of discharge. Date of admission and date of discharge will be recorded in the data for each study period. The sum of all ICU days for each subject will be calculated for the pre-treatment period and for the active treatment period. The number of ICU days for each admission will be calculated as follows (standardized to the number of days):

*Date of Discharge – Date of Admission + 1*

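### Hospital and ICU day totals count a date twice when two recorded stays share it; the SAP needs a merging rule and a stated day convention

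*SAP*

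**What the plan says.** Protocol 3.3.4.2 defines hospital length of stay by "calculating the number of days spent in the hospital for each admission, from time of admission to time of discharge", summed for each subject within each study period. ICU length of stay has the parallel definition. The protocol gives no formula for converting a stay into whole days. Its synopsis names the hospital endpoint "Number of inpatient hospital days".

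SAP 2.4.2.3.1 repeats the protocol's description and states what is available: "Date of admission and date of discharge will be recorded in the data for each study period". It names no clock times. Each hospital admission is scored as "Date of Discharge – Date of Admission + 1", and then "The sum of all hospital days for each subject will be calculated for the 6-month pre-treatment and active treatment periods". SAP 2.4.2.5.1 uses the same formula and the same summation for the ICU.

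Neither section says what to do when one stay ends on the date another begins. Neither says whether the result is to be read as calendar days or as elapsed time. The summaries (SAP 2.4.2.3.2 and 2.4.2.5.2) are descriptive, by period.

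**The concern.** An inclusive count is right for one stay taken alone, because it gives the number of calendar dates on which the patient was in hospital. It is not additive over stays that touch. If the discharge date of one record is the admission date of the next, each record claims that date and the sum holds it twice. Three ordinary events can produce such records: transfer between hospitals, readmission on the day of discharge, and leaving and re-entering the ICU on one day. ICU segments can then add up to more days than the hospital stay that contains them, which a reader of the tables would rightly see as impossible.

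There is also a point of interpretation. The inclusive total equals the number of midnights plus the number of admissions. A difference in mean days between periods therefore contains the difference in mean admissions, which the SAP already reports as a separate endpoint. A reader who takes the days as time in hospital should be told this.

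**Working it through.** The plan states no figure for this point, so there is nothing to reproduce. The check applies the SAP formula to constructed stays.

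**Inputs.** From SAP 2.4.2.3.1 and 2.4.2.5.1: days per stay = D − A + 1, with D the discharge date and A the admission date, summed over a subject's stays. The day numbers, clock times and admission counts below are assumed, because the documents give none.

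**Step 1, shared dates.** With k stays, Σ(D − A + 1) = Σ(D − A) + k. If s of the joins between consecutive stays fall on one date, the number of distinct calendar days is the SAP sum minus s.

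| Stays (day numbers) | SAP sum | Distinct calendar days | Midnights, Σ(D − A) |
|---|---|---|---|
| Hospital 1–8, one record | 8 | 8 | 7 |
| Hospital 1–5 and 5–8 | 5 + 4 = 9 | 8 | 7 |
| Hospital 1–3 and 3–8 | 3 + 6 = 9 | 8 | 7 |
| ICU 1–3 and 3–5 | 3 + 3 = 6 | 5 | 4 |
| ICU 1–3, 3–5 and 5–6 | 3 + 3 + 2 = 8 | 6 | 5 |
| Hospital 1–6, containing the ICU row above | 6 | 6 | 5 |

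The same eight days in hospital score 8 or 9 depending only on whether they are entered as one record or two. The last two rows give 8 ICU days within 6 hospital days. Counting distinct days gives 6 and 6.

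**Step 2, calendar days against elapsed time.** For 1,000,000 simulated stays of 1 to 9 nights, the excess of D − A + 1 over elapsed time was:

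- admission and discharge at any hour (uniform): mean 1.00 day, range 0 to 2;
- admission at any hour, discharge 10:00–16:00: mean 0.96 day;
- admission 12:00–24:00, discharge 10:00–16:00: mean 1.21 days.

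The excess is thus about one day per stay.

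**Step 3, what this does to a comparison of periods.** Assume 70 subjects and 210 nights in each period, with 70 admissions before and 50 on treatment. Mean nights are 210/70 = 3.00 in both periods. Mean inclusive days are (210 + 70)/70 = 4.00 and (210 + 50)/70 = 3.71. The difference of −0.29 comes wholly from (50 − 70)/70. If instead the mean stay is the same in both periods, the ratio of days is 50/70 = 0.714 under either count, so the relative change is unaffected.

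**The case against.** The strongest defence is that this is a choice of convention, applied consistently. The SAP also counts inclusively for antibiotic days (2.4.2.7.1) and days in study (2.2). The formula is the same in both periods. These endpoints have no planned test, paired difference or confidence interval, and admissions are summarised and listed separately. All of that stands, and it keeps the point small. It does not answer the shared date, which is counted twice even when a day means a calendar day.

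A fair reply is that double counting needs a transfer, same-day readmission or same-day ICU re-entry to be recorded as separate admissions, and the documents do not say that transfers are recorded that way. This also stands: the error is conditional. The SAP has no rule that prevents it.

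Three stronger readings are tempting, and the documents do not support them.

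- A reader might infer that the SAP contradicts the protocol by adding a day. The protocol asks for a number of days without a formula, and its synopsis speaks of inpatient days. Inclusive counting is one ordinary reading of that, so no departure is established and SAP section 3 need not declare one.
- A reader might infer that the + 1 should be deleted. A same-day stay would then score 0 days while still counting as an admission. With antibiotic days left inclusive, IV treatment throughout a stay on days 1–6 would score 6 IV days within 5 hospital days.
- A reader might infer that the formula exaggerates benefit by a known amount. The direction and size depend on admission counts and stay lengths that the documents do not give.

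**Conclusion.** The concern holds as a gap in the derivation. Summing inclusive days over stays adds one surplus day for each date shared by consecutive recorded stays, and ICU totals can exceed hospital totals. This follows from the formula itself and needs only that such stays are entered as separate admissions.

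The link between days and admissions is a matter of labelling. On a calendar-day definition a single stay is counted correctly; the extra day per stay appears only against elapsed time or midnights. It shifts a difference in mean days only when admission counts differ between periods, and the −0.29 above illustrates this under assumed counts. It is not an estimate for this trial.

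The effect is probably small and is confined to two secondary, descriptive endpoints. The primary endpoint is untouched.

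**What to change.** In SAP 2.4.2.3.1 and 2.4.2.5.1, keep the inclusive convention for a single stay and replace the sum over admissions with a count of dates. Total hospital days is the number of distinct calendar dates, per subject and study period, that fall within at least one recorded hospital stay, both end dates included. Total ICU days is defined in the same way from ICU stays. A shared date then counts once, and a same-day stay still counts as one day. The number of admissions is left as it is.

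Add one sentence, in the SAP and as a table footnote: totals are calendar days, which exceed elapsed time by about one day per stay, so a difference in mean days between periods partly reflects a difference in the number of admissions. This note is still needed after the change, because separate stays that do not touch each keep their extra day.

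The cost is a few lines of SAP text and about one line of code. It needs no new data, since the admission and discharge dates are already recorded.

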#### **2.4.2.3.2 Analysis of Hospital Length of Stay**

The number of inpatient hospital days will be analyzed descriptively by study period (active treatment and 6-month pre-treatment) using n, mean, standard deviation, minimum, median, and maximum.

#### **2.4.2.4 Number of ICU Admissions**

##### **2.4.2.4.1 Derivation of Number of ICU Admissions**

The number of ICU admissions that occurred during the pre-treatment period and active treatment period will be recorded in the data.

##### **2.4.2.4.2 Analysis of Number of ICU Admissions**

The number of ICU admissions will be analyzed descriptively by study period (active treatment and 6-month pre-treatment) using n, mean, standard deviation, minimum, median, and maximum. All ICU admissions that occurred in the 12-month pre-treatment period and the active treatment period will be listed.

#### **2.4.2.5 ICU Length of Stay**

##### **2.4.2.5.1 Derivation of ICU Length of Stay**

Total ICU length of stay will be determined for each study subject by summing the calculated number of days spent in the ICU for each admission, from time of admission to time of discharge. Date of admission and date of discharge will be recorded in the data for each study period. The sum of all ICU days for each subject will be calculated for the pre-treatment period and for the active treatment period. The number of ICU days for each admission will be calculated as follows (standardized to the number of days):

*Date of Discharge – Date of Admission + 1*

##### **2.4.2.5.2 Analysis of ICU Length of Stay**

Total ICU length of stay will be analyzed descriptively by study period (active treatment and 6-month pre-treatment) using n, mean, standard deviation, minimum, median, and maximum.

#### 2.4.2.6 Number of Outpatient Visits for Pulmonary Complication

##### 2.4.2.6.1 Derivation of Number of Outpatient Visits for Pulmonary Complication

The number of outpatient visits for pulmonary complication that occurred during the pre-treatment period and active treatment period will be recorded in the data.

##### 2.4.2.6.2 Analysis of Number of Outpatient Visits for Pulmonary Complication

The number of outpatient visits for pulmonary complication will be analyzed descriptively by study period (active treatment and 6-month pre-treatment) using n, mean, standard deviation, minimum, median, and maximum. All outpatient visits for pulmonary complication that occurred in the 12-month pre-treatment period and the active treatment period will be listed.

#### 2.4.2.7 Number of Antibiotic Use Days for Pulmonary Exacerbation

##### 2.4.2.7.1 Derivation of Number of Antibiotic Use Days for Pulmonary Exacerbation

Total number of antibiotic use days for pulmonary exacerbation will be determined by summing the calculated number of days of antibiotic use for each episode, from time of initiation to time of discontinuation. Date of initiation and date of discontinuation of antibiotic use for each pulmonary exacerbation will be recorded in the data for each study period. Antibiotic use will be further categorized and individual totals will be provided for 1) oral, 2) intravenous, and 3) nebulized antibiotic use for pulmonary complications that occur during the pre-treatment period and during the active treatment period. The number of antibiotic use days for each pulmonary exacerbation will be calculated as follows (standardized to the number of days):

$$\text{Date of Discontinuation} - \text{Date of Initiation} + 1$$

##### 2.4.2.7.2 Analysis of Number of Antibiotic Use Days for Pulmonary Exacerbation

The number of antibiotic use days for pulmonary exacerbation will be analyzed descriptively by study period (active treatment and 6-month pre-treatment) using n, mean, standard deviation, minimum, median, and maximum.

[figure not shown]
### **2.4.2.8 Quality of Life (QOL) Assessment**

#### **2.4.2.8.1 Derivation of Quality of Life (QOL) Assessment**

Severe Respiratory Insufficiency (SRI) questionnaire results for the Respiratory Complaints scale at baseline, 1-month, 3-month and 6-month study visits will be recorded in the data.

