3.3.3.1 Baseline Study Visit: During the baseline visit, study staff will review the informed consent form (and assent form if minor subject) with the study subject and/or caregiver(s). If the patient/caregiver agrees to participate in the study, the informed consent form (and assent form, if applicable) will be signed. A pregnancy test will be administered to female subjects of childbearing age. Inclusion and exclusion criteria will then be assessed and documented and (if eligible) the subject will be enrolled in the study. The study schedule and subject responsibilities will then be reviewed with the subject/caregiver. During the Baseline Visit, the subject's current respiratory therapy regimen and required respiratory support will be documented. A quality of life (QOL) assessment using the Severe Respiratory Insufficiency (SRI) questionnaire will be completed for each subject to assess QOL rating during the pre-treatment period and a Satisfaction Survey questionnaire will be completed by the subject and/or caregiver as an assessment of the current therapy regimen.

3.3.3.2 Documentation of Demographics, Medical History and Pulmonary Exacerbations: Demographic data will be collected for patients enrolled in the study. Medical records for each enrolled subject will be obtained and reviewed to obtain relevant patient medical history and to document pulmonary comorbidities and history at the time of enrollment. Current respiratory related medications and treatments will be documented. Pulmonary exacerbations (as defined in the study endpoints) that occurred in the 12-month period prior to enrollment in the study will be documented. Subsequent medical records will be obtained during the active treatment period and will be used to determine and to document the occurrence of pulmonary exacerbations during that period.

- **Demographic Data**

The following demographic data will be collected: Age, Height, Weight, Race, Ethnicity and Gender.

PROTOCOL TITLE

Evaluation of Oscillation and Lung Expansion (OLE) using The Volara® System for treatment of respiratory complications in patients with neuromuscular disease in the home setting

Final Protocol

Protocol Number: CR-RR-2020-005

Date: 11May2022

- **Pulmonary Related Medical History**

History of asthma, cystic fibrosis, bronchiectasis, COPD, obstructive sleep apnea, documented obesity (BMI $\geq 30 \text{ kg m}^2$), other pulmonary condition(s) will be documented.

- **Medications**

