Total number of Antibiotic Use Days for pulmonary exacerbation will be determined for each study subject by review of the medical record and by calculating the number of days of antibiotic use for each episode, from time of initiation to time of discontinuation. Antibiotic use will be further categorized and individual totals provided for 1) oral, 2) intravenous, and 3) nebulized antibiotic use for pulmonary complications that occur during the pre-treatment period and during the active treatment period. Total antibiotic days and totals for sub-categories will be determined for each subject and for the study group (Mean \pm SD) for each study period.

● Pulmonary Function Testing: Spirometry Measures, Oxygen Saturation and Maximal Inspiratory Pressure

Subject Pulmonary Function will be assessed at baseline and monthly during the active treatment period. Virtual visits will be conducted by pulmonary function specialists, as described above. The following measures will be collected:

- Slow Vital Capacity (SVC)
- Peak Cough Flow
- Resting SpO₂
- Maximal Inspiratory Pressure (MIP)

Baseline measures will be compared to measures obtained during the active treatment period.

● Quality of Life (QOL) Assessment

The Severe Respiratory Insufficiency (SRI) questionnaire will be administered to all study subjects by the study staff at baseline (reflecting pre-treatment therapy regimen) and during one-month, three-month and six-month study visits. Results will be determined for each subject and for the study group for each time period and will then be compared to determine any differences in QOL scores between the pre-treatment and active treatment time periods.

PROTOCOL TITLE

Evaluation of Oscillation and Lung Expansion (OLE) using The Volara® System for treatment of respiratory complications in patients with neuromuscular disease in the home setting

Final Protocol

Protocol Number: CR-RR-2020-005

Date: 11May2022

• Adherence to OLE Treatment Regimen

Adherence to the OLE treatment regimen will be determined by downloading device therapy log data during the active treatment period. Total adherence to the OLE treatment regimen will be determined for each subject and for the study group (Mean \pm SD) for the active treatment period.

• Patient/Caregiver Satisfaction with Therapy

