4. ICU LOS
5. Number of Outpatient Visits
6. Antibiotic Use Days
7. Pulmonary Function Testing
 - SVC
 - PCF
 - Resting SpO₂
 - MIP
8. QOL Assessment
9. Adherence to OLE Therapy Regimen
10. Patient/Caregiver Satisfaction

Comparison of Pre-treatment and Active Treatment Periods

Rate of exacerbation and health care utilization will be evaluated to compare the active treatment period and the control periods (six-month period immediately prior to active treatment and six-month seasonally equivalent time-period). Remaining endpoints will compare baseline assessments to assessments obtained during the active treatment period. Comparisons will be conducted for the purpose of identifying any statistical associations that can be attributed to use of OLE treatment with The Volara® System.

General Study Information**4.1 Technical Support for Device(s)**

Technical support will be performed by Hillrom following routine service practices (contact details will be provided).

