### 1.1 Study Objectives and Endpoints

The objective of the study is the evaluation of the impact of Oscillation and Lung Expansion (OLE) therapy to treat respiratory complications of neuromuscular disease in patients.

Primary Endpoint:

- Frequency of exacerbations of pulmonary disease requiring medical intervention (e. g. one or more of the following):
  - Hospitalization
  - Emergency Department (ED) Visit
  - Unscheduled Antibiotics for Respiratory Infection
  - Unscheduled outpatient visit

Secondary Endpoints:

- Pulmonary function tests
  - Slow Vital Capacity (SVC)
  - Peak Cough Flow (PCF)
  - Resting Oxygen Saturation (SPO2)
  - Maximal Inspiratory Pressure (MIP)
- Number of hospital admissions
- Total hospital length of stay
- Number of intensive care unit (ICU) admissions

- Total ICU length of stay
- Number of outpatient visits for pulmonary complication (Unscheduled Physician's office, Urgent Care Visits, ED visits)
- Number of antibiotic use days during episodes of pulmonary exacerbation
  - IV (intravenous) antibiotic days
  - Oral antibiotic days
  - Nebulized antibiotic days
- Quality of Life (QOL) Assessment
- Patient/caregiver satisfaction with therapy

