### Guidance for scoring

Please provide the following values for each item:

completely untrue	=>	1
mostly untrue	=>	2
sometimes true	=>	3
mostly true	=>	4
always true	=>	5

The majority of items need to be recoded following the instructions given below:

value	recoded value	Items which need to be recoded:
1	→ 5	
2	→ 4	
3	→ 3	
4	→ 2	
5	→ 1	1, 2, 4, 5, 6, 8, 11, 12, 13, 14, 15, 16, 17, 19, 21, 22, 23, 24, 25, 26, 28, 29, 30, 31, 34, 35, 38, 39, 40, 42, 43, 45, 46, 47, 48.

Next, the scales need to be calculated as indicated below. For this purpose at least 50% of the items per scale must be correctly addressed. Please find the item number indicated in brackets [a, b, c.....]. This process of transformation produces a score between 0 and 100 with higher values indicating a better health-related quality of life according to content of the scale.

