## 3. CHANGES FROM ANALYSIS PLANNED IN PROTOCOL

Mean adherence to prescribed treatment regimen will not be analyzed.

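### The SAP narrows the protocol's SRI quality-of-life endpoint to the 8-item Respiratory Complaints scale, does not list this in Section 3, and so supports no general quality-of-life statement

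*SAP*

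**What the plan says.** **Protocol.** Section 3.3.3.1 (Baseline Study Visit) names the instrument: "A quality of life (QOL) assessment using the Severe Respiratory Insufficiency (SRI) questionnaire will be completed for each subject". Section 3.3.4.2, under the QOL endpoint, repeats it: "The Severe Respiratory Insufficiency (SRI) questionnaire will be administered to all study subjects by the study staff at baseline", and again at the 1-, 3- and 6-month visits. Results are then to be "compared to determine any differences in QOL scores between the pre-treatment and active treatment time periods". No scale is singled out, and no summary score or primary scale is named. Section 3.5.2 lists QOL among the secondary endpoints to be summarised descriptively. It adds, for the period comparisons as a whole: "Comparisons will be conducted for the purpose of identifying any statistical associations that can be attributed to use of OLE treatment".

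**SAP.** The endpoint list in Section 1.1 carries the unrestricted label "Quality of Life (QOL) Assessment". Section 2.4.2.8.1 then states that SRI "questionnaire results for the Respiratory Complaints scale at baseline, 1-month, 3-month and 6-month study visits will be recorded in the data". Section 2.4.2.8.2 plans descriptive statistics and change from baseline for that scale's score, plus response frequencies for its individual items. The scoring guidance reproduced there says "the scales need to be calculated as indicated below", in the plural, but only the Respiratory Complaints formula follows. The QOL outputs in Appendix 1 (Tables 14.2.4.1 and 14.2.4.2, Listings 16.2.6.4.1 and 16.2.6.4.2) all concern Respiratory Complaints. Section 3, on changes from the protocol, has one entry: "Mean adherence to prescribed treatment regimen will not be analyzed".

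**The concern.** A named secondary endpoint is broader in the protocol than in the SAP, and the section meant to record such differences is silent on this one. That section was used to declare that the adherence endpoint is dropped, so a reader relying on it would take the QOL endpoint to be unchanged.

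What is at stake is what the report may say. The study is open label and single-arm, compares each subject before and after, and takes QOL from a questionnaire. If one symptom scale moves and is reported as the QOL endpoint, the reader cannot see whether the rest of the questionnaire moved with it, stayed flat or got worse. This matters in a descriptive study too, because the protocol intends its comparisons to bear on the effect of OLE.

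**Working it through.** The plan gives no figure to reproduce here: the sample of about 70 is a convenience sample, and no effect size, SD, alpha or power is stated for QOL. The check is a comparison of text and a count of items.

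**1. Scope, document by document**

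| Element | Protocol | SAP |
|---|---|---|
| Instrument | SRI questionnaire (3.3.3.1, 3.3.4.2) | SRI, Respiratory Complaints scale only (2.4.2.8.1) |
| Visits | Baseline, 1, 3, 6 months | Same |
| Quantity | QOL scores, scale not specified | One scale score and its items (2.4.2.8.2) |
| Endpoint name | QOL assessment | QOL assessment (1.1), unrestricted |
| Declared as a change | – | Not in Section 3 |

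The visits and the name agree. The content does not.

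**2. How much of the instrument is analysed** (inputs from the scoring guidance in SAP 2.4.2.8.2)

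- Items in Respiratory Complaints: 2, 5, 12, 19, 22, 24, 25, 29, which is 8 items.
- Items in the recode list: 35, the highest numbered 48. The total is not stated, so the questionnaire has at least 48 items.
- Share analysed: at most 8/48 = 16.7%.
- A lower bound follows from the guidance's remark that most items are recoded. If 35 is more than half, the total is below 70, and the share is at least 8/69 = 11.6%.
- All 8 items are in the recode list, so 35 − 8 = 27 recoded items enter no planned analysis. Nor do the 48 − 35 = 13 item numbers up to 48 that are not recoded. Together that is 27 + 13 = 40 items, at least.

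**3. Is the one formula sound?** The score is (mean − 1)/4 × 100. A mean of 1 gives (1 − 1)/4 × 100 = 0, and a mean of 5 gives (5 − 1)/4 × 100 = 100, which matches the stated 0–100 range. The 50% completion rule requires 4 of the 8 items. The scale itself is correctly specified.

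**4. Can one scale stand for the whole?** The guidance ties the meaning of each score to the content of its own scale. On the SAP's own source, a Respiratory Complaints score describes respiratory complaints. No summary score across scales is defined in the SAP.

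**The case against.** The strongest reply is that this is a documentation gap in one secondary endpoint of a descriptive pilot. The protocol promises neither an overall SRI score nor a list of scales. The SAP plans no formal tests, the table and listing titles already name the scale, and a summary of a named scale supports a statement about that scale. All of that stands. Only the endpoint list in SAP 1.1 and the heading of 2.4.2.8 are unqualified. Even so, the reply does not restore the rest of the endpoint or explain why Section 3 omits the restriction.

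A reader might infer more than the documents allow:

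- **That the scale was picked because of its results.** SAP version 2.0 is dated 28 May 2024, about two years after the protocol version it rests on (11 May 2022). That does not show that data had been seen. The contents page lists a revision history whose text is not in the copy available to me. Version 1.0 may already have had the restriction, perhaps with a reason. Non-declaration is therefore verified for Section 3 only.
- **That an inflated chance of a favourable finding can be calculated.** The SAP plans no confidence interval or test for QOL; its only planned interval is for the primary paired difference. The number of scales is not given, and scales from one questionnaire in the same subjects are unlikely to be independent.
- **That the retained scale favours the device and the others would show harm.** The wording of the items is not shown and no other scale is named, so this would be guesswork.
- **That data already collected are being discarded.** The protocol has the whole questionnaire administered, but SAP 2.4.2.8.1 leaves unclear whether the other items were captured.

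**Conclusion.** The concern holds in limited form. Followed as written, the SAP analyses one 8-item scale, at most 16.7% of the protocol's QOL instrument, under an endpoint label that has not been narrowed, and Section 3 does not list the restriction. The planned output supports a conclusion about respiratory complaints. It does not support one about quality of life in general, and unchanged or worse results on other SRI scales would not appear.

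It would go too far to say that the trial can support no QOL-related conclusion, or that reporting has been shown to be selective. The size rests on one reading: that items numbered to 48 mean at least 48 items. The count of at least 40 unused items also assumes that the full SRI was given as the protocol says. The primary analysis is unaffected.

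**What to change.** First state in SAP 2.4.2.8 whether the full SRI was captured. Then:

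- **If it was:** score every scale in the scoring guide already cited, and a summary score if that guide defines one, at baseline, 1, 3 and 6 months with change from baseline. Keep Respiratory Complaints as one row. The other formulas must be brought in from the guide, since the SAP reproduces only one.
- **If only the 8 items were captured:** rename the endpoint 'SRI Respiratory Complaints scale' in SAP 1.1 and in the 2.4.2.8 heading. List the restriction in Section 3 with its reason and its timing relative to any review of the data, and limit conclusions to that scale. The table and listing titles already name it.

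The cost is a longer table with some added scoring code in the first case. In the second it is a relabelled endpoint, a short entry in Section 3 and a narrower claim. Neither needs new data collection.
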